### **Measures (See Table 3)**

Measurement will include survey-based assessments, targeted qualitative interviews, observational implementation assessment, and EHR data on service delivery of SEEK (e.g., rate of screening) and CM.

### **Organizational Assessment**

Organizational measures will be administered at baseline regarding the opportunity to adopt SEEK. Practice leaders and PCPs who decide to participate in the study will be recruited; those who opt out will be asked to complete the one-time brief online SEEK Adoption Survey and the following 4 measures. A subsample will undergo a semi-structured, 30-minute phone interview.

**Demographics Form.** This includes the healthcare system and practice structure, annual budget, number of practices, number and characteristics of PCPs, presence of behavioral health and patient demographics.

**Evidence-Based Practice Attitude Scales (EBPAS).** The 15-item EBPAS measures 4 domains of service providers' attitudes toward adopting EBPs: *appeal* (the extent to which one would adopt an EBP if it is appealing), *requirements* (willingness to adopt an EBP if required to do so), *openness* (general openness to new interventions), and *divergence* (the degree to which one believes that EBPs are less important than clinical experience). Subscales have adequate internal consistency (Cronbach's  $\alpha = .67\text{-.91}$ ) and convergent validity.

**Implementation Leadership Scale (ILS).** The 12-item ILS assesses leader support for EBPs within an organization (5-point Likert scale). Four subscales - *proactive*, *knowledgeable*, *supportive*, and *perseverant* leadership - have excellent internal consistency ( $\alpha = .95$  to  $.96$ ), and convergent and discriminant validity.

**Implementation Climate Scale (ICS).** The 18-item ICS assesses how the organization views new interventions. Implementation climate is defined as shared perceptions of policies, practices, procedures and behaviors that are rewarded, expected and supported. The measure has strong psychometrics with internal consistency ( $\alpha = .81\text{-.91}$ ), convergent validity, and validation in a sample of child welfare professionals.

### **Implementation Process and Outcomes**

The **Stages of Implementation Completion (SIC)** is an observational assessment tool developed in a large randomized implementation trial. The SIC has 8 stages, each including sub-activities, extending from Engagement with the developers to achievement of practitioner Competency. Each stage maps onto 3 phases of implementation (Pre-Implementation, Implementation and Sustainment). Competency is viewed as *entering* into the Sustainment phase. Sustainment is an ongoing process toward achievement of Stage 8.

The SIC has been adapted for over 20 different implementation strategies involving varied interventions. These multiple adaptations led to the development of the empirically derived *Universal SIC*, with items found to be relevant and reliably utilized across each of the adaptations, regardless of service sector or population (e.g., child welfare, primary care, prevention). The Universal SIC spans the 8 original SIC stages, with 45 activities tracked during implementation. For the current study, completion of activities will be monitored by the practice manager and collected monthly by the research team, with data entered into the SIC data collection website. The website is managed by the SIC team, and through a web-based tool, implementation performance at the practice level can be benched against other implementation efforts.

**SIC Scores.** Three scores are calculated for each SIC stage. First, the time that a practice takes for a stage is calculated (Duration Score). Because the implementation process is nonlinear, the Duration Score takes into account activities that may not be completed sequentially within a stage. If a site completes only one activity in

a stage, the Duration Score for that stage is a single day. Duration Scores are calculated separately for each stage due to the potential for overlap across stages; the total Duration Score does not necessarily equal the summation of each stage's Duration. Rather, the total Duration Score is calculated from the date of the first completed SIC activity to the final activity completed, regardless of the stage in which it occurred. Second, the percentage of activities completed within a stage is calculated Proportion Score). Similar to Duration,

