**Aim 2. Examine variations in SEEK's implementation process and impacts and understand associated barriers and facilitators in pediatric and family medicine practices.** We will determine the proportion of practices that agree to adopt SEEK. We will then quantitatively assess the relationship between practice characteristics (e.g., demographics, EBP attitudes) and willingness to adopt SEEK. The most important independent predictors will be determined using multivariable logistic regression models. Among those that do adopt SEEK, we will assess their degree of completeness, speed, and quality of implementation using the SIC. Completeness will be summarized using the final stage attained (0-8). Speed will be summarized by the duration in each stage, and quality by the proportion of activities performed at each stage, and overall. The distribution of these variables will be determined, overall and separately, based on the type of

practice. The distribution of time to achieve each phase will be estimated using the Kaplan-Meier approach. Barriers and facilitators to implementing SEEK will be probed quantitatively and qualitatively (see below). Among practices adopting SEEK, we will examine the association between practice characteristics and measures of completeness, speed, and quality of implementation from the SIC. We will examine relationships between practice characteristics and implementation by comparing the distribution of SIC scores in groups defined by practice characteristics. Finally, the most important predictors of degree of implementation will be determined using multivariable regression models with practice characteristics as predictors and SIC measures as outcomes. In addition to studying implementation at the practice level, we will analyze the relationship between PCP level measures of implementation (e.g., screening rates) and PCP characteristics, facilitators and barriers. These models will account for clustering of PCPs within practices, as described above.

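### Aim 2 measures speed by a stage duration that early stopping or skipping shortens, so characteristics linked to non-completion can look linked to faster implementation

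*Combined protocol and SAP*

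**What the plan says.** The SIC is described in the protocol under Implementation Process and Outcomes. For each stage, "the time that a practice takes for a stage is calculated (Duration Score" being the name given to the result. The same paragraph adds that if a site completes only one activity in a stage, "the Duration Score for that stage is a single day". For the whole process, "the total Duration Score is calculated from the date of the first completed SIC activity to the final activity completed". Two other scores are kept separately: the proportion of activities completed, and the last stage reached.

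The Data Analysis Plan, Aim 2, turns these scores into outcomes. The population is stated as follows: "Among those that do adopt SEEK, we will assess their degree of completeness, speed, and quality of implementation using the SIC". The measure of speed is fixed: "Speed will be summarized by the duration in each stage". Completeness is the final stage and quality is the proportion of activities. Among adopting practices, "we will examine the association between practice characteristics and measures of completeness, speed, and quality of implementation from the SIC". SIC score distributions are to be compared between groups defined by practice characteristics, and the section ends with "multivariable regression models with practice characteristics as predictors and SIC measures as outcomes". A Kaplan-Meier analysis is planned for the time to reach each phase (stages 1-3, 4-7 and 8).

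No sentence limits the duration analyses to practices that completed the stage, treats an unfinished stage as censored, or analyses duration together with the proportion completed.

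**The concern.** A Duration Score is the elapsed time between activities that were done. It says nothing about activities that were not done. A short value can mean that a practice finished the stage quickly, that it began and stopped, or that it skipped most of the stage and moved on. The one-day rule is the extreme case, and as a scoring convention it is harmless. The difficulty arises when Aim 2 reads the score as speed and compares it across practices regardless of whether the stage was completed.

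Aim 2 exists to find barriers to and facilitators of start-up and sustainment. If a characteristic makes practices stop early or skip activities, it also shortens their recorded durations. It can then show up in the speed analysis as going with faster implementation. That is a systematic distortion, and adding practices would not remove it.

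**Working it through.** The documents give no figure to reproduce. Nothing in Table 4 uses Duration Scores; its only Aim 2 entry is the precision of the adoption proportion. The check is of the scoring rule, followed by an illustration on assumed inputs.

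**Step 1: the scoring rule.** I read the stage score as an inclusive span, last completed-activity date minus first, plus 1. The documents do not print this formula, but it reproduces their one-day rule.

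| Pattern in one stage | Calculation | Score |
|---|---|---|
| One activity, then nothing | 0 − 0 + 1 | 1 day |
| Two activities 10 days apart, then nothing | 10 − 0 + 1 | 11 days |
| All activities, day 0 to day 59 | 59 − 0 + 1 | 60 days |

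One day is the minimum, tied only with a practice that completes the stage within a single day. The 11-day practice did not finish either, yet scores lower than the one that did. The total Duration Score also ends at the last activity done, so stopping early shortens it too.

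**Step 2: effect on a group mean.** Let *s* be the share of practices with exactly one activity in the stage and *D* the mean duration of the others, taken as completers. Then mean = (1 − *s*) × *D* + *s* × 1. Both *s* and *D* are assumptions, because the documents give neither. For *D* = 60:

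- *s* = 10%: 0.9 × 60 + 0.1 × 1 = 54.1 days
- *s* = 20%: 0.8 × 60 + 0.2 × 1 = 48.2 days
- Difference 5.9 days; ratio 48.2 / 54.1 = 0.89

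Completers are equally fast in both groups, yet the group with twice the share of one-activity practices has a mean 11% lower. Over a range of *D*:

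| Assumed *D* | Mean, *s* = 10% | Mean, *s* = 20% | Mean, *s* = 30% | Gap, 10% v 20% | Gap, 10% v 30% |
|---|---|---|---|---|---|
| 30 | 27.1 | 24.2 | 21.3 | 2.9 | 5.8 |
| 60 | 54.1 | 48.2 | 42.3 | 5.9 | 11.8 |
| 120 | 108.1 | 96.2 | 84.3 | 11.9 | 23.8 |

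**Step 3: the planned group sizes.** The Sample section plans 13 pediatric and 35 family medicine practices, 48 in all. Suppose two practices in each group do one activity in a stage and every other practice takes 60 days (assumed):

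- Pediatric: (11 × 60 + 2 × 1) / 13 = 662 / 13 = 50.9 days
- Family medicine: (33 × 60 + 2 × 1) / 35 = 1,982 / 35 = 56.6 days

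The pediatric mean is about 10% lower (50.9 / 56.6 = 0.90), although that group has the higher one-activity share (2/13 = 15% v 2/35 = 6%).

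**The case against.** There is a fair case that this matters less than it might seem.

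- **Few practices may score one day.** The Universal SIC has 45 activities over 8 stages, about 5.6 per stage, and only a stage with exactly one completed activity gets the minimum. A reader might infer that stalled practices in general are analysed as the fastest. The documents do not support that: a practice that stops after two or more activities gets a truncated span, which is too short but need not be the shortest.
- **One activity is not proof of stalling.** The protocol calls the process nonlinear and allows stages to overlap, so a practice may have skipped activities and moved on. This stands. One day is still not a measure of how fast that practice completed the stage.
- **Other measures sit alongside.** Final stage and proportion of activities are reported, phases have a Kaplan-Meier analysis, and barriers are also studied through interviews. These would help a careful reader notice the problem. They do not correct the stage-level comparisons, and the Kaplan-Meier analysis is planned for phases without being tied to predictors.
- **The regression sentence does not name duration.** It speaks of SIC measures in general. The sentence on associations names "measures of completeness, speed, and quality of implementation from the SIC", so the use of speed as an outcome is explicit there and only implied in the regressions.
- **The sign of the Aim 2 findings.** A reader might infer that conclusions on barriers will be reversed. The illustrations do not show this: they start from equal speed among completers and produce a spurious gap. A reversal would need a true difference smaller than the spurious one, and the documents give neither.

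**Conclusion.** The concern holds for the stage-level speed measure in Aim 2 and the analyses built on it. As planned, duration combines quick completion with early stopping and skipping, and characteristics associated with non-completion can appear associated with faster implementation.

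The size is unknown. The figures above rest on assumed completion times and one-activity shares, and they treat all other practices as completers. They show the direction of the distortion and how it scales, and they do not estimate it. Aim 1, the Aim 3 pre-post comparison and the power table do not use Duration Scores and are unaffected. The change is worth making before analysis because it corrects a stated rule at low cost.

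**What to change.** In the Data Analysis Plan, Aim 2, redefine speed as time to stage completion:

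1. Pre-specify what counts as completing each stage. The SIC text sets no threshold, and because activities may be skipped, the criterion should say which activities, or what proportion of them, are required.
2. Start the clock at the first activity in the stage, or at a common start date. The common date has the advantage of keeping in practices that never began the stage.
3. Keep practices that do not meet the criterion at risk, censored at the end of the observation period (month 41 for cohort 1, month 48 for cohort 2, under Procedures, Sustainment Phase). Do not censor at last contact: losing contact and stalling are likely to be related, which would make the censoring informative.
4. Use Kaplan-Meier curves by group and Cox models with few predictors, given 48 practices.
5. Report the raw Duration Score only descriptively, among practices that completed the stage, next to the proportion completing it.

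No new data are needed: activity completion is already collected monthly and the Duration Score already requires dates. The costs are agreeing a completion criterion, revising the analysis wording, and accepting that stage-level models will be sparse.

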**Table 3: Study Measures Related to Specific Aims**

Domain/Measure	Aims	Respondent*	Baseline** A: mo 8 B: mo 15	Training A: by mo 9 B: by mo 10	F/U 1 A: mo 20 B: mo 27	F/U 2 A: mo 29 B: mo 30	F/U 3 A: mo 41 B: mo 48
Organizational							
System Demographics	1, 2, 3	SL	●			●	
Evidence Based Practice Attitude Scale	1, 2, 3	All, except parents	●		●	●	●
Implementation Leadership Scale	1, 2, 3	All, except parents	●		●	●	●
Implementation Climate	1, 2, 3	All, except parents	●		●	●	
Implementation Process							
Stages of Implementation	2, 3	AS	●	●	●	●	●
Adoption							
SEEK Adoption Survey	2, 3	SL, PL, PCP	●				
Seek Training							
SEEK Training Evaluation	1, 2, 3	PCP		●			
Child Maltreatment							
EHR review****		IT			●		●
Implementation Outcomes							
SEEK PCP Questionnaire	1, 2, 3	PCP	●	●	●	●	●
SEEK PCP Survey	1, 2, 3	PCP		●	●	●	●
SEEK Office Staff	1, 2, 3	AS		●	●	●	●
SEEK Parent View	1, 2, 3	P		●	●	●	●
Rate of Screening	1, 2, 3	EHR	●	●	●	●	●
Receipt of Services	1, 2, 3	EHR	●	●	●	●	●
Costs							
Cost of Implementing New Strategies (COINS)	2, 3	PL, AS, PCP			●	●	●
General							
Qualitative Phone Interviews	1, 2, 3	All		●	●	●	●

\*SL = system leaders, PL = practice leaders, PCP = primary care providers, BHP = behavioral health professionals, AS=ancillary staff, P=parents, BHP=behavioral health professional, IT=information technology

\*\*A = 1st cohort of healthcare systems and practices, B = 2nd cohort of healthcare systems and practices

\*\*\*\*Brief Child Abuse Potential Inventory, \*\*\*\*EHRs will be reviewed by IT toward end of study

Proportion Scores are calculated separately for each stage. The total Proportion Score is based on the number of activities completed out of the number that could be completed – for each stage.

Finally, the SIC Stage Score marks the final stage that a site reaches. SIC scores are calculated within each of the three Implementation Phases: Pre-implementation (stages 1-3), Implementation (stages 4-7), and Sustainment (stage 8).

### **SEEK Targeted Adoption, Training, Implementation Assessment**

**SEEK Adoption Survey.** This survey will capture key considerations regarding decisions whether to adopt SEEK, including perceived barriers and strengths.

**SEEK PCP Training Evaluation Form.** This online survey will be developed to evaluate PCPs' perceptions of the training approaches and solicit input as to how the training might be improved.

**SEEK PCP Questionnaire.** (PCPQ). The PCPQ, used in both SEEK RCTs, has 5 vignettes, with 7-12 statements assessing PCPs' thinking and practice with regard to addressing the targeted CM risk factors. Each vignette is followed by statements such as "I know how to motivate parents who may be resistant to suggestions" rated on a Likert scale. Items were grouped conceptually into 4 topical scales (e.g., Substance Abuse) and also cross-cutting themes (e.g., Perceived Competence). Cronbach's alphas were adequate for most scales: Depression (.76), IPV (.80), Major Stress (.80) and Substance Abuse (.58), and for most themes: Attitudes (.77), Knowledge (.55), Comfort (.68), Competence (.74) and Practice (.70).

**SEEK PCP Survey.** This 19-item measure uses a 5-point Likert scale to assess PCPs' experience implementing SEEK including their perceptions of its relevance, ease of delivery, helpfulness and training.

**Survey.** This 23-item measure uses a 5-point Likert scale to assess staff experiences with SEEK, including how they understood their roles and perceived competence in implementing SEEK.

**Rate of Screening.** EHR data on the proportion of eligible visits where screening occurred, in a given period.

**Receipt of Services.** EHR data on referrals and receipt of services by parents with positive screens.

**SEEK Parent View of Child's PCP.** Parents rate their child's PCP on this measure adapted for pediatric practice from the Patient-Doctor Interaction Scale; reliability and validity are good. The Likert scale was changed to a yes-no response. Individual scores range from 0 – 20; higher scores indicate greater satisfaction.

### **Child Maltreatment**

**EHR CM-related Diagnoses.** ICD-10 codes related to CM are readily accessible through EHRs. De-identified aggregate data will be gathered toward study end for all children 0-5 attending the practices during the study – for up to 2 years prior to and during the study.

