**Aim 2. Evaluate the impact of inner context variables (e.g., variation between pediatric and family medicine) on the SEEK implementation process and understand associated barriers and facilitators to successful service start-up and sustainment of SEEK delivery.** Using a mixed methods approach, standardized measures of the implementation process (Stages of Implementation Completion; SIC) and associated cost (Cost of Implementing New Strategies; COINS), will be integrated with qualitative interview data focusing on barriers and facilitators during implementation from exploration to sustainment. Variations in adoption, model fidelity, and sustainment, and the economic ramifications of each of the SEEK training and implementation strategies will be examined.

**Aim 3. Examine the effectiveness of the intervention strategies in preventing CM.** CM will be measured via prevalence of ICD-10 codes related to CM obtained from electronic health records for all children 0-5 attending the practices. **H1.** Incidence of CM will be reduced in practices after implementing SEEK. **H2.** Practices randomized to MOC training that successfully implement SEEK, will have lower incidences of CM than with the IND approach. We will also probe the influence of *SEEKonline* and the Traditional approach on CM rates. Additionally, implementation success, will be examined in relation to CM prevalence rates.

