**Final 12 months.** De-identified aggregate data will be obtained from practices' EHRs on all children (0-5) for the periods prior to and during SEEK implementation: rate of eligible visits where screening occurred, types of problems identified, types of actions taken, receipt of services, as well as CM-related diagnoses using ICD-10 codes. This will be facilitated by 4 of the 5 systems using EPIC as their EHR and having in-house IT. The data will be analyzed, the Final Report prepared, and presentations and papers will continue to be developed.

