**Aim 3. Examine the effectiveness of SEEK in reducing CM.** As in our previous studies, we will identify CM-related diagnoses, now via EHRs. We will review the EHR for each child (0-5) in each practice for two years prior to implementing SEEK and during implementation. The presence of CM-related ICD-10 codes will be recorded. The proportion of children with CM diagnoses before and during SEEK will be compared at each practice. Formal inference regarding the best estimate and statistical significance of pre-post differences will be based on a binary regression model with a random effect for site, similarly to Aim 1.

**Sample Size Considerations.** Our projected sample sizes (numbers of practices, professionals within each practice, and children in the practices) should provide good precision to estimate parameters and ample power to detect moderate associations. Table 4 below shows the detectable effect sizes for various comparisons, based on performing 2-sided .05-level tests and incorporate a 1.5-fold increase in variance and sample size to account for potential loss of power due to clustering of observations within practices and systems. In general, the detectable effect sizes are moderate, at plausible levels. We observed effect sizes of about 1.0 regarding Competence and Comfort in SEEK II. For Aim 2, assuming 90% of practices provide organizational information, we will estimate the rate of adoption of SEEK accurately,  $\pm$  15 percentage points.

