**Table 4. Power Calculations**

Aim	Respondents/Source	Measure	N per group	Detectable Effects with 80% power
1a	PCPs	Changes in Comfort and Competence in addressing CM	137	Effect size  of 0.42
1a	Parents	Parent satisfaction	144	Effect size  of 0.41
1b	Staff	Staff Perceptions	24/72 	Effect size  of 0.82
2	Practices	Proportion adopting	59	Precision of +/- 15 pct points
3	EHR	Pre-post prevalence of CM-related diagnoses	98,000	5% vs. 4.5%  10% vs. 9.6%

Defined as the difference in means between groups divided by the standard deviation.

Conservatively assuming an imbalance between SEEKonline vs. Traditional of as much as 25% to 75%.

In our previous evaluations of SEEK, we observed rates of CM in the medical record ranging from 5% to 1%.

methods.

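### The plan does not settle which children form the pre-SEEK side of the maltreatment endpoint, and its look-back wording, if followed, would bias the Aim 3 pre-post test in an unstated direction

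*Combined protocol and SAP*

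**What the plan says.** Three places describe the Aim 3 population.

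- Measures, Child Maltreatment: data are collected "for all children 0-5 attending the practices during the study – for up to 2 years prior to and during the study". The first part selects children; the second sets how far back their data go.
- Procedures, final 12 months: "De-identified aggregate data will be obtained from practices' EHRs on all children (0-5) for the periods prior to and during SEEK implementation".
- Data Analysis Plan, Aim 3: "We will review the EHR for each child (0-5) in each practice for two years prior to implementing SEEK and during implementation".

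The contrast is then stated as "The proportion of children with CM diagnoses before and during SEEK will be compared at each practice", and inference "will be based on a binary regression model with a random effect for site, similarly to Aim 1". No age term or exposure-time term is named for Aim 3. The hypothesis at stake is Aim 3 H1: "Incidence of CM will be reduced in practices after implementing SEEK".

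None of these places says who is in the pre-period denominator, how children who left or aged out are handled, or whether the measure is per child or per unit of child-time.

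**The concern.** A child seen only in the pre-SEEK years never attends during the study. Under the Measures wording that child is not selected, and any earlier maltreatment code is lost. A child born after SEEK starts is selected but has no pre-SEEK time. The two sides of the comparison are then formed by different rules, even when the windows are equally long.

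The Aim 3 test compares proportions of children without adjusting for age or time observed, so nothing in the named model would absorb the asymmetry. The data arrive as de-identified aggregates in months 49-60. If the query is built on the wrong population, the returned counts may not allow a correction afterwards.

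**Working it through.** **Yardstick from the plan.** Table 4, Aim 3, gives 5% vs 4.5% as detectable, a ratio of 4.5/5 = 0.90, under the column "Detectable Effects with 80% power" with 98,000 per group. The calculations are "based on performing 2-sided .05-level tests and incorporate a 1.5-fold increase in variance and sample size". The usual two-proportion formula is n = [z(0.975)·√(2p̄q̄) + z(0.80)·√(p1q1 + p2q2)]² / (p1 − p2)². It gives 28,408 per group for 5% vs 4.5%, and × 1.5 = 42,612. At 98,000 per group with the 1.5 factor, power is 98.9% for this pair and 68.1% for 10% vs 9.6%, so the row does not reproduce. That is a separate matter; I use 0.90 only as the size of effect the plan has in view.

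**Inputs from the documents.** The pre window is two years, so W = 24 months. SEEK starts in month 9 (cohort 1) or month 16 (cohort 2), so 8 or 15 study months precede it.

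**Assumptions, because the documents give no figures.** One birth per month, no migration, every child of eligible age attends, a constant code rate, no SEEK effect, and a during-SEEK window also of 24 months. Ages 0-5 are taken as an upper limit L of 60 or 72 months. At low proportions the chance of a code is close to proportional to time observed.

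**Formulas.** Let g be the number of months before SEEK from which attendance qualifies a child: 0 if the study is read as the SEEK period, 8 or 15 if counted from study month 1.

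- Full pre child-time = L·W. During child-time is the same.
- Pre child-time lost with children who aged out before selection began = (W − g)²/2.
- Pre child-time kept, K = L·W − (W − g)²/2.
- Same cohort as denominator on both sides: ratio = L·W / K.
- Children not yet born excluded from the pre denominator: ratio = [L·W/(L + W)] / [K/(L + g)].
- Period-specific populations: L + W children and L·W child-months in each period, so ratio = 1.00.

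**Example (L = 72, g = 0).** L·W = 1,728; lost = 24²/2 = 288; K = 1,440 (83.3% kept). Of 72 + 24 = 96 selected children, 24 (25%) were born after SEEK started. Same denominator: 1,728/1,440 = 1.20. Born children only: (1,728/96)/(1,440/72) = 18/20 = 0.90.

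| g (months) | L (months) | K / full pre child-time | Ratio, same cohort both sides | Ratio, unborn excluded from pre |
|---|---|---|---|---|
| 0 | 60 | 1,152 / 1,440 | 1.25 | 0.89 |
| 0 | 72 | 1,440 / 1,728 | 1.20 | 0.90 |
| 8 | 60 | 1,312 / 1,440 | 1.10 | 0.89 |
| 8 | 72 | 1,600 / 1,728 | 1.08 | 0.90 |
| 15 | 60 | 1,399.5 / 1,440 | 1.03 | 0.92 |
| 15 | 72 | 1,687.5 / 1,728 | 1.02 | 0.93 |

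Replacing the proportional approximation by 1 − exp(−rate × time), scaled so that the full pre-period proportion is 5%, gives the same ratios to two decimals.

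**Child-time rate.** With a constant code rate, the look-back rate per child-month equals the rate in all children, and the artefact disappears. It returns if risk varies with age. With g = 0, tripling the rate in the first year of life (assumed) shifts the pre rate by +5% to +7%; doubling it after age 3 (assumed) shifts it by −7% to −11%. Leaving that is related to maltreatment would also bias it; I have not quantified that.

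**The case against.** The strongest reply is that the look-back cohort is only one reading. The Procedures and the Aim 3 analysis text make no condition of later attendance, and item 3 of the Introduction to Proposal likewise speaks of all children in the participating practices. Period-specific populations fit those passages at least as well and would remove the bias. This stands: the documents do not support treating the look-back cohort as the settled design. But those passages neither override the Measures definition nor define the pre denominator, so whoever writes the query has to choose.

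A reader might go further in four ways that the documents do not support.

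- *That unborn children are counted on the pre side, so a true reduction is always hidden.* No passage says so. Leaving them out is equally compatible with the wording and reverses the sign.
- *That the false increase is 20-25%.* That holds only if selection starts with SEEK. The wording refers to the study, which begins 8 or 15 months earlier, and the figure then drops to 2-10%.
- *That a child-time rate would not help.* Under a constant code rate it removes the artefact.
- *That Table 4's single 98,000 shows one set of children serving both periods.* A stable practice census would give the same number in each period.

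**Conclusion.** The plan describes the Aim 3 population inconsistently and leaves the pre-period denominator undefined. If the Measures wording is followed, the H1 contrast is biased even with equal windows. With no SEEK effect, the during/pre ratio ranges from about 0.89 to 1.25, against a planned ratio of 0.90. The upper values would mask a real reduction or show an increase; the lower ones would look like the planned benefit with none present. Which occurs depends on a choice that the plan does not state.

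These sizes rest on steady births, no migration, a constant code rate and 24-month windows; only the timing of SEEK and the two-year look-back come from the documents. The artefact should be similar in MOC and IND practices, so the randomized comparison in Aim 3 H2 is largely unaffected.

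The timeline implies 32 months of SEEK in each cohort (41 − 9 and 48 − 16) against 24 before. That imbalance is a separate issue. Equalising the windows would not cure this one, nor would the fix below cure the imbalance.

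**What to change.** Reconcile the Child Maltreatment measure, the final-12-months procedure and the Aim 3 analysis text by defining both populations with one rule:

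- Pre-SEEK population: every child aged 0-5 with a visit to the practice in the pre-SEEK window, whether or not seen later.
- SEEK population: every child aged 0-5 with a visit in the SEEK window.
- In each period, count only codes dated within that window while the child is 0-5.
- Have IT return numerators and denominators by age year for each period, so that the comparison is age-standardised.

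The cost is about a sentence in each affected section and a slightly larger EHR query that includes children no longer attending. It should be settled before the extraction in months 49-60.
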